7.3.3 FOLLOW-UP

Visit 3, Day 0+2 days

Subjects will be examined 2-3 days after treatment for the occurrence of adverse events. Vital signs and any changes in concomitant medication will be recorded. Subjects will be discharged from the clinic and will be instructed to return for the Month 1 assessment and treatment.

Visit 4, Month 1 (\pm 7 days)

Subjects will return to the clinic one month after the first treatment. Adverse events, vital signs and any changes to concomitant medications will be recorded.

Subjects will receive treatment as described in section 7.3.1. Following treatment, the investigator will examine the treated area and report immediate and short term response. Subjects will complete the 10 cm discomfort/pain VAS immediately after treatment.

Subjects will be discharged from the clinic and will be instructed to return in 2-3 days in order to be examined for adverse events.

Visit 5, Month 1+2 days

Subjects will be examined 2-3 days after treatment for the occurrence of adverse events. Vital signs and any changes in concomitant medication will be recorded. Subjects will be discharged from the clinic and will be instructed to return for the Month 2 assessment and treatment.

Visit 6, Month 2 (\pm 7 days)

Subjects will return to the clinic one month after the second treatment. Adverse events, vital signs and any changes to concomitant medications will be recorded.

Subjects will receive treatment as described in section 7.3.1. Following treatment, the investigator will examine the treated area and report immediate and short term response. Subjects will complete the 10 cm discomfort/pain VAS immediately after treatment.

Subjects will be discharged from the clinic and will be instructed to return in 2-3 days in order to be examined for adverse events.

Visit 7, Month 2+2 days

Subjects will be examined 2-3 days after treatment for the occurrence of adverse events. Vital signs and any changes in concomitant medication will be recorded. Subjects will be discharged from the clinic and will be instructed to return for the Month 3 assessment.

Visit 8, Month 3 (\pm 7 days)

Subjects will return to the clinic one month after the third treatment. Adverse events, vital signs and any changes to concomitant medications will be recorded.

Photographs of the treated area will be taken as described in section 7.3.1. Subjects will be discharged from the clinic and will be instructed to return for the Month 4 assessment.

Visit 9, Month 4 (\pm 7 days)

Subjects will return to the clinic one month after the last assessment. Adverse events, vital signs and any changes to concomitant medications will be recorded.

Photographs of the treated area will be taken as described in section 7.3.1. Subjects will be discharged from the clinic and will be instructed to return for the Month 5 assessment.

Visit 10, Month 5 (\pm 7 days)

Subjects will return to the clinic one month after the last assessment. Adverse events, vital signs and any changes to concomitant medications will be recorded. Subjects will complete a 5-point Likert satisfaction questionnaire and the POSAS.

Photographs of the treated area will be taken as described in section 7.3.1. Subjects will be discharged from the clinic and will be instructed to return for the final Month 12 assessment.

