7.3 STUDY SCHEDULE

7.3.1 SCREENING

Visit 1, Day -1 (Skin Types I-III) or Day -5 (Skin Type IV)

Point of enrollment

Point of enrollment is defined as the point where the patient, after having signed the informed consent form, is confirmed to fulfill all criteria for eligibility.

Following the point of enrollment, each subject will receive study treatment and study questionnaires.

Screening Visit

If the subject meets the preliminary study criteria, the study doctor, and/or his/her designee, will obtain an informed consent from the subject prior to any study procedure, clearly indicating his/her understanding of the requirements and possible risks associated with study participation and other applicable treatment options.

During the first visit, the study investigator, and/or his/her designee, will screen the subject for eligibility to participate in the clinical study using the inclusion/exclusion criteria. A urine sample for the pregnancy test will be obtained (in patients of child-bearing potential). During screening, the study doctor will review the subject's medical/surgical history and examine the subject's targeted area to ensure that it meets the study criteria. The subject will complete screening and the treatment will be scheduled.

During the first visit, the investigator will ask women of child-bearing potential for the date of their last period, if not applicable the investigator shall inquire about the form of contraceptive they use to confirm they meet the inclusion criteria.

Test Spots

A small test spot will be performed in a non-conspicuous area of the treatment site, prior to the first complete session. Test spots are performed to establish the following requirements:

- Confirm the patient's suitability for treatment: For skin types I-III wait 24-48 hours before assessing the skin response and 5-7 days for skin type IV.

- Establish and confirm treatment parameters: If the desired endpoint of erythema and edema – in a tip-shaped pattern – has not been achieved within 10-15 minutes, increase the RF indicator level and perform another test spot. If the response is excessive, decrease the parameters and perform another test spot.

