- Treat the untreated patches of skin as normally.

Fine-tuning of the parameters should be done before proceeding to treatment of the entire sub-area with the selected parameters. Treatment consists of a single pass over the designated area. The applicator tip should be placed on the skin, a pulse emitted, then lifted and moved to an adjacent spot of the skin. The emitted pulses should create tip-shaped patterns. Leave, no untreated gaps between the pattern marks, while also being careful not to overlap the treated zones. The parameters can be modified during subsequent visits, as per the practitioner's discretion.

Post-Treatment Care

Post-treatment cooling is not necessary. In the event of post-treatment discomfort, it is recommended to cool the treated area immediately with air cooling. Cold (not frozen) packs may also be used.

Blistered or ulcerated skin can be treated with a prescribed cream. Tiny scabs of less than 1 mm diameter will usually form 24-72 hours post-treatment and may remain for several days. The scabs should not be touched or scratched even if they itch, and should be allowed to shed off naturally. Blistered or ulcerated skin can be treated with a prescribed antibiotic ointment or burn treatment cream as per physician's discretion. During the first two days following treatment, care should be taken to prevent trauma to the treated site. Hot baths, massage, etc. should be avoided. The skin should be kept clean to avoid contamination or infection. Any mechanical or thermal damage to the area must be avoided. Moisturizer may be applied only 24 hours after each treatment, and then should be applied regularly throughout the course of the treatment. Make-up may be applied only 24 hours after each treatment if desired, unless an unwanted reaction occurs in the area. Generally, 24 hours after treatment, patients may use regular soaps, but not scrub soaps or exfoliants. The patient should use a high-factor sunscreen (at least 30 SPF) and protect the treated area from sunlight for at least one month after the treatment. Tanning of any sort (sun exposure, tanning beds, and artificial sunless tanning lotions) is not allowed in the treated areas during the entire course of the treatment. Tanning after treatment may cause hyperpigmentation.

The patient should return 1-2 days for skin types I-III or 5-7 days for skin type IV after the test spot treatment to ensure that no adverse events have occurred.

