7.3.7 SCHEDULE OF EVENTS TABLE

Procedures	Screening/Baseline (Visit 1, Day -1)	Enrollment/Treatment (Visit 2, Day 0)	Follow-up (Visit 3, Day 0+2 days)	Treatment & Follow-up (Visit 4, Month 1 (± 7 days))	Follow-up (Visit 5, Month 1+2 days)	Treatment & Follow-up (Visit 6, Month 2 (± 7 days))	Follow-up (Visit 7, Month 2+2 days)	Follow-up (Visit 8, Month 3 (± 7 days))	Follow-up (Visit 9, Month 4 (± 7 days))	Follow-up (Visit 10, Month 5 (± 7 days))	Final Study Visit (Visit 11, Month 12 (± 14 days))
Informed consent	X										
Inclusion/exclusion criteria	X	X									
Demographics	X										
Medical history	X										
Physical exam	X										
Vital signs		X	X	X	X	X	X	X	X	X	X
Urine pregnancy test ^a	X										
Test Spot	X										
Photographs		X						X	X	X	X
Administer Treatment		X		X		X					
Discomfort/Pain VAS	X		X		X						
PI immediate & short-term response	X		X		X						
Blinded reviewer GAIS		X						X	X	X	X
Blinded reviewer MSS	X							X	X	X	X
Blinded reviewer POSAS	X									X	X
Subject POSAS	X									X	X
Subject satisfaction questionnaire										X	X
Concomitant medication	X	X	X	X	X	X	X	X	X	X	X
Adverse event evaluation		X	X	X	X	X	X	X	X	X	X

Procedures	Screening/Baseline (Visit 1, Day -1)	Enrollment/Treatment (Visit 2, Day 0)	Follow-up (Visit 3, Day 0+2 days)	Treatment & Follow-up (Visit 4, Month 1 (± 7 days))	Follow-up (Visit 5, Month 1+2 days)	Treatment & Follow-up (Visit 6, Month 2 (± 7 days))	Follow-up (Visit 7, Month 2+2 days)	Follow-up (Visit 8, Month 3 (± 7 days))	Follow-up (Visit 9, Month 4 (± 7 days))	Follow-up (Visit 10, Month 5 (± 7 days))	Final Study Visit (Visit 11, Month 12 (± 14 days))
^a For women of child-bearing potential.											

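### The Schedule of Events puts the test spot on Day -1 with no skin-type distinction, while section 7.3.1 gives Day -5 and a 5-7 day reading interval for skin type IV

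*Combined protocol and SAP*

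**What the plan says.** Section 5.3 excludes Fitzpatrick types 5-6, so type IV subjects can enrol.

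Section 7.3.1 treats type IV separately in three places:
- The visit heading: "Visit 1, Day -1 (Skin Types I-III) or Day -5 (Skin Type IV").
- The test-spot instructions, under confirming suitability for treatment: "For skin types I-III wait 24-48 hours before assessing the skin response and 5-7 days for skin type IV".
- The end of the post-treatment care text: "The patient should return 1-2 days for skin types I-III or 5-7 days for skin type IV after the test spot treatment", to check that no adverse events have occurred.

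The Schedule of Events in section 7.3.7 heads the first column "Screening/Baseline (Visit 1, Day -1"). It has no Day -5 entry, and its only footnote concerns women of child-bearing potential. The test spot is marked in that column and nowhere else. The next column is Visit 2, Day 0, when the first full treatment is given.

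For the period after each full treatment, section 7.3.3 says of Visits 3, 5 and 7: "Subjects will be examined 2-3 days after treatment for the occurrence of adverse events". The heading of the first of these is "Visit 3, Day 0+2 days". Neither is split by skin type. The next scheduled visit after Visit 3 is "Visit 4, Month 1 (± 7 days"), where, as at the later monthly visits, "Adverse events, vital signs and any changes to concomitant medications will be recorded".

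**The concern.** The test spot is the protocol's check that a subject can tolerate the device before a full treatment. For type IV, section 7.3.1 sets a longer wait before that check is read. The schedule table is what a site is likely to use for booking, and it drops the longer wait. If the table is followed, the first full treatment of a type IV subject comes before the interval in section 7.3.1 has passed, and the suitability check is then not the one the protocol describes.

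A related question arises after treatment. The early adverse-event check at 2-3 days is the same for all skin types, although the test-spot return is not. Treatment-related adverse events by 10 months are a safety endpoint (section 4.2.2), so it matters whether transient reactions are seen directly or only reported later.

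**Working it through.** This is a comparison of stated days; there is no plan figure to reproduce.

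**1. Test spot to first full treatment, type IV (Visit 2 = Day 0)**

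| Source | Test spot | Days to Visit 2 |
|---|---|---|
| 7.3.1 heading | Day -5 | 0 - (-5) = 5 |
| 7.3.1 test-spot and return text | not given as a day | 5-7 |
| 7.3.7 table | Day -1 | 0 - (-1) = 1 |

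The heading and the text of 7.3.1 agree at the lower end of the range. The table does not agree with either. Its shortfall against 5-7 days is 5 - 1 = 4 to 7 - 1 = 6 days. The table shows no visit between Visits 1 and 2, so no other column could carry the type IV return.

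For types I-III there is no conflict: Day -1 gives 1 day, within the 24-48 hours (1-2 days) stated.

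**2. Examinations after a full treatment (secondary observation)**

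- The early check is at days 2-3 (text) or day 2 (visit heading). The test-spot interval for type IV is days 5-7. The two windows do not overlap; the second opens 5 - 3 = 2 days after the first closes.
- The next visit is one month ± 7 days, counted from the preceding treatment as section 7.3.3 words it. With a 30-day month (an assumption) that is day 30 - 7 = 23 to day 30 + 7 = 37.
- The gap without a scheduled examination is therefore 23 - 3 = 20 to 37 - 2 = 35 days. For months of 28 to 31 days the range is 28 - 7 - 3 = 18 to 31 + 7 - 2 = 36 days.
- No scheduled visit falls on days 5-7 after any of the three treatments.

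**3. How many subjects**

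The documents do not say how many type IV subjects are expected. The maximum enrolment is 50 + 25 = 75. If 10% to 40% were type IV (an assumption), that is 7.5, rounded up to 8, to 30 subjects. Each has one test-spot interval (point 1) and up to three full treatments, hence 24 to 90 sessions (point 2). The true number could be zero.

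**The case against.** On the table, the other side can say that section 7.3.1 gives the type IV interval three times, so a site would have to overlook all three to treat early. That is fair: the error is not certain to occur, and the correction is small. But the table remains in conflict with the text on a pre-treatment suitability check, and nothing in the protocol says which prevails.

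On the post-treatment checks, a reader might infer that the protocol needs 5-7 days to read any type IV skin reaction, so that the examination at 2-3 days is too early and adverse events are under-counted. The documents do not support that:
- Both statements of 5-7 days concern the test spot. No section applies them to a full treatment.
- Section 7.3.1 says small scabs usually form 24-72 hours after treatment, which gives the 2-3 day visit a basis of its own.
- That visit is not the only safety check. The investigator also examines the area immediately and at 30 minutes (7.3.2), and adverse events are recorded at the monthly and later visits.
- Every visit asks about events since the last one (8.3), unscheduled visits are provided for (7.3.6), and any burn is reported to the sponsor within 24 hours (7.8).
- The endpoint counts subjects with a treatment-related event by 10 months, so an event reported at a later visit still counts.

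Moving the 2-3 day visit would also give up the early check, which is a clinical trade-off. What stands is narrower. The test-spot return and Visits 3, 5 and 7 share the purpose of looking for adverse events, yet only the former distinguishes skin types, and no reason is given. A transient reaction around days 5-7 would be known from recall or self-referral, with some risk of under-grading.

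**Conclusion.** The mismatch between sections 7.3.1 and 7.3.7 is wrong as written. For type IV the table gives 1 day from test spot to first treatment, against 5 days in the heading of 7.3.1 and 5-7 in its text. It affects type IV subjects only, and only where the site follows the table rather than the text. It is a minor inconsistency in extent, but it sits on a safety step.

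The uniform 2-3 day check is an observation for the sponsor to confirm. It is not an internal contradiction, and the documents do not show that the adverse-event endpoint is under-ascertained. The 20-35 day gap assumes a 30-day month. The number of subjects affected is unknown.

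**What to change.** Reconcile the Visit 1 timing in sections 7.3.1 and 7.3.7 so that text and table give the same skin-type-dependent interval, by a revised column header or a footnote. The sponsor decides the clinical timing; this review takes no position on which interval is right.

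At the same time, the sponsor should state whether Visits 3, 5 and 7 are meant to be the same for all skin types, and give the reason if so.

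The cost is one table edit and one sentence. Under section 13.2 any protocol amendment needs ethics committee or IRB approval before it is implemented, so the edit is best bundled with another change if one is pending. No added visit is needed to reconcile the table.

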The investigator will examine the treated areas and report immediate and short term response (30 minutes post-treatment) (pain during treatment, hemorrhage, burn, erythema, edema, purpura) using a 5-point scale: 1=none; 2=trace; 3=moderate; 4=marked; 5=severe.

The assessment of discomfort/pain based on the subject's completion of the 10 cm VAS should also be documented immediately after each treatment.

The normal response to these treatments is transient erythema and edema. If any other side effects occur, as indicated in the protocol, they must be recorded.

Subjects will be discharged from the clinic and will be instructed to return in 2-3 days in order to be examined for adverse events.

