8.3 TIME PERIOD AND FREQUENCY FOR EVENT ASSESSMENT AND FOLLOW-UP

The occurrence of an AE or SAE may come to the attention of study personnel during study visits and interviews of a study participant presenting for medical care, or upon review by a study monitor. All AEs including local and systemic reactions not meeting the criteria for SAEs will be captured on the appropriate CRF. Information to be collected includes event description, time of onset, clinician's assessment of severity, relationship to investigational device and study procedures (assessed only by those with the training and authority to make a diagnosis), and time of resolution/stabilization of the event. All AEs occurring while on study must be documented appropriately regardless of relationship. All AEs will be followed to adequate resolution.

Any medical condition that is present at the time that the participant is screened will be considered as baseline and not reported as an AE. However, if the study participant's condition deteriorates at any time during the study, it will be recorded as an AE.

Changes in the severity of an AE will be documented to allow an assessment of the duration of the event at each level of severity to be performed. AEs characterized as intermittent require documentation of onset and duration of each episode.

The PI will record all adverse events with start dates occurring any time after informed consent is obtained. At each study visit, the investigator will inquire study subjects about the occurrence of AE/SAEs since the last visit. All adverse events need to be followed until resolution or until study end, whichever occurs first.

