10.4.4 SAFETY ANALYSES

The safety analysis will be done by analyzing spontaneous reports of adverse events (AE), subjects' completed 10 cm discomfort/pain VAS and a response questionnaire as well as analysis of immediate and short term response reports by the principal investigator from his/her observation/examination of the treated area. Appropriate Medical Dictionary for Regulatory Activities (MedDRA) code will be used to describe all spontaneously reported or other study related adverse events.

Summaries of spontaneously reported or other study related adverse events will be presented as:

- Number (%) of subjects with any AE,
- Number (%) of subjects with any serious adverse events (SAE),
- Number (%) of subjects permanently withdrawn from treatment due to AE

Summaries of analysis of immediate and short term response reports by the principal investigator examination will be displayed on a bar or pie chart as;

- the overall frequency of subjects with each event (pain during treatment, hemorrhage, burn, erythema, edema, purpura)
- Frequency of subjects with specific severity/intensity for each event using a 5 points scale: 1=none; 2=trace; 3=moderate; 4=marked; 5=severe
- The overall percentage or proportion of subject observed with marked or severe intensity of any event will be calculated and compared to those with none, trace or moderate severity/intensity with the aid of a bar or pie chart.

The following will be considered for the analysis of 10 cm discomfort/pain VAS scores safety data:

Summary table for differences of baseline post-treatment (Visit 2) and Visit 6 post-treatment 10 cm discomfort/pain VAS scores will be displayed as mean difference, standard deviation and standard error. The 10 cm discomfort/pain VAS is a 11-level (0 to 10) ordinal scale tool for assessing pain.

Bar, pie charts or graphs indicating scores, percentages or proportions of subjects with Visit 6 and baseline (Visit 2) post-treatments VAS scores difference that is < 1 and > 1 will be used to analyse subjects' tolerability of this treatment.

All statistical tests will be two-sided. The level of statistical significance for effectiveness analyses is 5% ($\alpha = 0.05$) for all tests of differences. Where appropriate, Paired t-test and/or Wilcoxon Signed-Ranks Test

for Matched Pairs will be used to compare the difference between Visit 2 and Visit 6 post treatment VAS scores.

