11 SOURCE DOCUMENTS AND ACCESS TO SOURCE DATA/DOCUMENTS

Each participating site will maintain appropriate medical and research records for this trial, in compliance with ISO 14155:2011, and regulatory and institutional requirements for the protection of confidentiality of participants. Each site will permit authorized representatives of the study sponsor, ethics committee and/or regulatory agencies to examine (and when permitted by applicable law, to copy) clinical records for the purposes of quality assurance reviews, audits, and evaluation of the study safety, progress, and data validity.

Source data are all information, original records of clinical findings, observations, or other activities in a clinical trial necessary for the reconstruction and evaluation of the trial. Examples of these original documents and data records include, but are not limited to, hospital records, clinical and office charts, laboratory notes, memoranda, participants' memory aids or evaluation checklists, pharmacy dispensing records, recorded audio tapes of counseling sessions, recorded data from automated instruments, copies or transcriptions certified after verification as being accurate and complete, microfiches, photographic negatives (where applicable), microfilm or magnetic media, x-rays, and participant files and records kept at the pharmacy, at the laboratories, and medico-technical departments involved in the clinical trial.

It is acceptable to use CRFs as source documents. The following CRFs collected on no carbon required (NCR) paper will be source documents:

- Independent blinded reviewer POSAS
- Subject self-reported POSAS

- Subject self-reported VAS and 5-point Likert satisfaction questionnaire
- Investigator reported immediate (immediately post-treatment) and short term (30 minutes after treatment) safety response

The remainder of the data collected from other sources.

It is not acceptable for the CRF to be the only record of a subject's participation in the study. This is to ensure that anyone who would access the patient medical record has adequate knowledge that the patient is participating in a clinical trial.

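### The 5-point skin response is graded only after treatment at Visits 2, 4 and 6, so erythema or edema already on a young scar can be counted as that day's response

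*Combined protocol and SAP*

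**What the plan says.** - **When the skin is graded.** Section 7.3.3 (Visits 4 and 6) states "Following treatment, the investigator will examine the treated area and report immediate and short term response". Section 7.3.2 uses the same sentence for Visit 2.
- **What is graded.** Section 7.3.2 lists pain during treatment, hemorrhage, burn, erythema, edema and purpura, "using a 5-point scale: 1=none; 2=trace; 3=moderate; 4=marked; 5=severe". It adds: "The normal response to these treatments is transient erythema and edema".
- **What the form holds.** The source-document list in section 11 describes it as "Investigator reported immediate (immediately post-treatment) and short term (30 minutes after treatment) safety response". No entry before treatment is listed.
- **How it is analysed.** Section 10.4.4 plans "Frequency of subjects with specific severity/intensity for each event using a 5 points scale", and then "The overall percentage or proportion of subject observed with marked or severe intensity of any event will be calculated". Both use the post-treatment grade alone; no change from an earlier grade is mentioned.
- **Who is treated.** Inclusion criterion 2 in section 5.2 admits subjects from four weeks after surgery.

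**The concern.** A grade called a response is read as something the device did that day. A surgical scar four weeks old may already be red or slightly swollen before the applicator touches it. If the only grades are taken afterwards, such a sign enters the table in the same way as a new one.

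The summaries at stake are the frequency of each sign, its severity distribution, and the proportion of subjects with a marked or severe grade. Safety is half of the study's stated objective, and these tables describe how the skin tolerates each session. A grade not taken before treatment cannot be reconstructed at analysis.

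**Working it through.** The plan states no figure on this point. The check is whether any other record supplies a grade of the same signs, on the same scale, before that day's treatment.

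| Record | Where | What it gives | Same-scale grade before treatment? |
|---|---|---|---|
| Physical examination at Visit 2 | 7.3.2 | General examination before the first treatment | No |
| Photographs | 7.3.2, 7.3.7 | Taken before the first treatment at Visit 2; none on the day at Visits 4 and 6 | No |
| Test-spot check | 7.3.1 | Skin reaction judged at 24-48 hours (types I-III) or 5-7 days (type IV) | No |
| Adverse event inquiry | 8.3 | New events, and worsening of a baseline condition | No |
| Examination 2-3 days after treatment (Visits 3 and 5) | 7.3.3 | Adverse events | No |
| Untreated half of the scar | 7.3.2 | Visible control, but the 5-point form covers only the treated area | No |

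The adverse event rule needs both of its halves. A condition present at screening "will be considered as baseline and not reported as an AE", but if it deteriorates it is recorded as one. In addition, "At each study visit, the investigator will inquire study subjects about the occurrence of AE/SAEs since the last visit". So worsening can be captured, while stable redness of a young scar stays out of the adverse event data. That stable redness is what could enter the response table.

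**Why post-treatment grades alone cannot settle it.** Let b be the share of subjects who already have at least a trace of a sign, and t the share of the others who develop it after treatment. If every sign seen is graded, the tabulated frequency is

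F = b + (1 - b)t.

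Two assumed pairs, chosen only to show the ambiguity:

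- b = 0.10, t = 0.30: F = 0.10 + 0.90 × 0.30 = 0.37
- b = 0.30, t = 0.10: F = 0.30 + 0.70 × 0.10 = 0.37

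The same table entry fits a true response of 30% or of 10%. The excess over the true response is F - t = b(1 - t). It is never negative and is zero when b = 0, so the direction is upward. Its size needs b, which the documents do not give and the plan does not collect.

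**Which signs.** Pain during treatment has no value before treatment. Hemorrhage, burn and purpura are unlikely to be present beforehand except as a remnant of an earlier session. Erythema and edema are where a prior grade matters.

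**The case against.** The strongest reply is that the investigator is asked for a response, which already implies judging change. The untreated half of the same scar is in view at that moment and can serve as a reference. The test spot is small, a single pulse, and is checked before the first full session. The protocol calls the usual reaction transient, so carry-over from a session a month earlier should be slight. Any bias makes the device look worse rather than better, and no test or decision rule rests on these grades. The case report form is not among the documents, and chart notes on the skin before treatment may exist.

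Most of this stands, and it keeps the point small. It does not remove it. The plan neither tells the investigator to discount earlier signs nor records whether that was done, so a reader cannot tell which convention a grade follows. Unstructured notes would not give a grade that could be tabulated beside the planned ones.

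Three stronger readings are tempting, and the documents do not support them:

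- **That subjects could be re-treated at Visits 4 and 6 over an active skin condition or a recent tan with nothing to prevent it.** Exclusions 12 and 17 are formally re-confirmed only up to Visit 2. However, adverse events are asked about at every visit, tanning is forbidden during the treatment course, and the area is shaved where needed and the energy set to suit it. Exclusion 18 and section 5.5.1 also let the investigator stop. A further tick-box would be a documentation preference.
- **That no photograph precedes the later treatments.** The Visit 2 photographs do; only a same-day photograph is missing.
- **That the inflation can be put at so many percentage points.** Any such figure would rest on assumed rates alone.

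**Conclusion.** The point holds as a minor one. At Visits 2, 4 and 6 the planned grades cannot by themselves separate that day's erythema or edema from what was already there, and no other scheduled record supplies a same-scale grade beforehand. The likely effect is an overstated frequency and an overstated marked-or-severe proportion. The amount cannot be estimated from the documents, and it is nil if no subject has such signs beforehand or if the investigator discounts them consistently.

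Two assumptions carry this conclusion: that some scars near the four-week limit are visibly red or swollen, which is clinically plausible but not quantified in the protocol; and that the investigator grades what is seen. The consequence is limited to descriptive safety summaries. A reader should not infer that the safety analysis as a whole is unsound or that the primary endpoints are affected. Those endpoints come from a separate blinded reviewer using other scales.

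**What to change.** 1. At Visits 2, 4 and 6, before any pulse that day (including a repeat test spot), grade at least erythema and edema in the area to be treated, on the existing 5-point form.
2. Add this entry to sections 7.3.2 and 7.3.3, the schedule in 7.3.7 and the source list in section 11.
3. In section 10.4.4 keep the planned absolute post-treatment frequencies, so that a lasting effect of an earlier session is not hidden. Add the pre-treatment grades and the number (%) of subjects whose grade worsened from before to after treatment.

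The cost is a small form change and a few minutes per treatment visit, by an investigator who is already present. With two signs at three visits, this adds 2 × 3 = 6 grades per subject, beside the 2 signs × 2 times × 3 visits = 12 already planned for erythema and edema. No extra visit is needed.
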